4.3 IBD activity assessment

Validated Mayo score evaluates ulcerative colitis stage, based on four parameters (full Mayo score): stool frequency, rectal bleeding, endoscopic evaluation and physician's global assessment (see **Appendix 3**). Each parameter of the score ranges from zero (normal or inactive disease) to 3 (severe activity). The partial Mayo score uses the three non-invasive components of the full Mayo Score (stool frequency, rectal bleeding and Physician's global assessment). This excludes the score for the endoscopic findings; therefore, the maximum score is reduced from 12 to 9 points. The full or partial Mayo score (in accordance with routine clinical practice) will be evaluated at each study visit.

Harvey-Bradshaw index (HBI) is used in the assessment of Crohn's disease activity (see **Appendix 4**). It is a validated clinical index for CD, including the 5 categories of: general well-being, abdominal pain, number of liquid stools, abdominal mass and complications. The score ranges from 0 to 25 with higher scores indicating higher disease activity. The scores were classified as follows: less than 5 is remission, 5 to 7 is mild, 8 to 16 is moderate, and greater than 16 is severe. HBI will be evaluated at each study visit.

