Statistical methods

All data from patients enrolled in this study will be analysed. Information on CD and UC patients will be presented separately. Also, analysis will be performed separately by therapy subgroups (patients receiving non-biological therapy and patients receiving biological therapy). Due to complexity of treatment regimen a manual review can be used to define treatment subgroup for each patient.

A descriptive analysis approach will be used to analyse the data and the study outcomes for the different study subgroups.

Descriptive statistics will include summary tables (n, mean, median, standard deviation, minimum and maximum, lower and upper quartile for continuous variables and n, frequency and percentage for categorical values). Proportion will be assessed together with 95% confidence interval, if applicable. Cross tabulations will be used to present study outcomes by the corresponding subgroups, when required. Time to event will be described with Kaplan-Meier estimates. Median time to event will be presented together with the lower and upper quartiles. Baseline and retrospective data will be used to describe the patient population and will be tabulated separately.

The number and percentage of patients who have reached remission while in the study will be presented. Selected outcomes will be reported separately for those who have reached remission and those who haven't. Mayo and HBI scores data will be analyzed according to the scales definitions.

Laboratory data will be reported in terms of frequency and percentage of abnormal findings.

In general, all data will be listed, sorted by type of disease (UC and CD), site and patient number, and when appropriate by visit number within patient.

3 Table of Contents

Contents

1	Administrative information	2
1.1	Contacts	2
1.2	Approval	3
2	Study summary	4
3	Table of Contents	10
4	List of Abbreviations and Definition of Terms	14
4.1	List of Abbreviations	14
4.2	Definition of Terms	16
4.3	IBD activity assessment	17
4.4	Treat to target approach in IBD treatment	17
5	Introduction	17
5.1	Background	17
5.2	Rationale	18
6	Study Objectives and outcomes	19
6.1	Study objectives	19
6.2	Study outcomes	20
7	Study Administrative Structure	21
7.1	Steering Committee	21
7.2	Study Sites	22
7.3	Sponsor Personnel	22
7.4	Contract Research Organisation	23
7.5	Essential Documents	24
8	Ethical and Legal aspects	24
8.1	Ethical conduct of the Study	25
8.2	Independent Ethics Committee	25

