Appendix 3. Mayo score

The full Mayo Score evaluates ulcerative colitis stage, based on four parameters: stool frequency, rectal bleeding, endoscopic evaluation and Physician's global assessment (1,2). Each parameter of the score ranges from zero (normal or inactive disease) to 3 (severe activity). The following table indicates, for each parameter, the input values with their respective scores.

Parameter	Clinical evaluation (single choice)	Score
1. Stool frequency (per day)	
 normal number of stools 1-2 more than normal 3-4 more than normal ≥ 5 more than normal 	0 1 2 3
2. Rectal bleeding (indicate the most severe bleeding of the day)	
 none streaks of blood with stool in less than half of the cases obvious blood with stools in most cases blood alone passes 	0 1 2 3
3. Endoscopic findings	
 normal mucosa or inactive disease mild activity (erythema, decreased vascular pattern, mild friability) moderate activity (marked erythema, lack of vascular pattern, friability, erosions) severe activity (spontaneous bleeding, large ulcerations) 	0 1 2 3
4. Physician's global assessment	
 normal mild disease moderate disease severe disease 	0 1 2 3

Calculation formula: sum of the scores of the four parameters.

Score	Decoding
0 - 2	Remission (provided that no subscore for each single parameter is greater than 1)
3 - 5	mild activity
6 - 10	moderate activity
> 10	severe activity

Partial Mayo Score uses the three non-invasive components of the full Mayo Score (stool frequency, rectal bleeding and Physician's global assessment). This excludes the score for the endoscopic findings, therefore the maximum score is reduced from 12 to 9 points (1,2). This simplified index maintains a good relationship with the full Mayo Score in identifying clinical response as perceived by patients (3).

Score	Decoding
<2	remission
2 - 4	mild activity
5 - 7	moderate activity
> 7	severe activity

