### Subgroups of first-line biological therapy

1. Vedolizumab
  - a. By the period of time from diagnosis to biological therapy prescription:
    - up to 2 years inclusive
    - from 2 to 5 years inclusive
    - more than 5 years
  - b. By the number of courses of systemic corticosteroids in medical history before biological therapy prescription:
    - < 3 courses
    - ≥ 3 courses

Protocol ID	MACS-2017-102279	STATISTICAL ANALYSIS PLAN	Page 18 of 41	
IP	N/A		Date	30.12.2021
ID	MACS-2017-102279_SAP		Version	v1.2 final

c. Depending on disease activity at the moment of biological therapy prescription:

- Crohn's disease, the Harvey-Bradshaw index:

- < 5 points
- 5-16 points
- >16 points

- Ulcerative colitis, the Partial Mayo Score:

- 0 scores
- 1-2 scores
- 3-5 scores
- ≥ 6 scores

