- Average maximum dose for each component of the combination (across all courses);
- Average number of courses per patient;
- Total duration of use of each combination / course for the total duration of observation (retro- and prospective);
- Distribution of each pattern by subgroups: age, gender, region, duration of the disease, disease activity (according to Visit 1 Mayo / Harvey-Bradshaw indices).

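### UC activity class can depend on whether endoscopy was done, because the SAP does not fix the Mayo version; separately, the SAP 7.4 partial-Mayo bands cross the protocol's partial-Mayo classes

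*Protocol*

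**What the plan says.** Protocol 4.3 leaves the choice of UC score to the site: "The full or partial Mayo score (in accordance with routine clinical practice) will be evaluated at each study visit". It notes that the partial version omits endoscopy, and "therefore, the maximum score is reduced from 12 to 9 points". In Protocol 12.3 and 12.4 endoscopic findings are recorded only if an endoscopy was done. The footnote to the 12.2 table limits all examinations to those made in routine practice.

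Appendix 3 gives each version its own class table:

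| Class | Full Mayo (0–12) | Partial Mayo (0–9) |
|---|---|---|
| Remission | 0–2, with no subscore above 1 | below 2 |
| Mild | 3–5 | 2–4 |
| Moderate | 6–10 | 5–7 |
| Severe | above 10 | above 7 |

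The condition in the full-score remission row reads "Remission (provided that no subscore for each single parameter is greater than 1".

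The Statistical methods part of the Protocol Study summary says "Mayo and HBI scores data will be analyzed according to the scales definitions". SAP 8.1.2 breaks the treatment patterns down by "disease activity (according to Visit 1 Mayo / Harvey-Bradshaw indices", and SAP 8.1.3 tabulates Mayo activity at Visits 1, 2 and 3. Neither names the version.

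SAP 7.4 does name one. Under "Ulcerative colitis, the Partial Mayo Score" it sets bands of 0, 1–2, 3–5 and ≥6, repeated for each first-line drug group. The SAP history of changes shows that these subgroups came in with version 1.2, after an interim analysis.

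**The concern.** If each patient is classed by whichever version was scored, two patients with identical symptoms and physician assessment can land in different classes because one was scoped. Endoscopy follows the physician's decision, and Visits 2 and 3 may be remote contacts (Protocol 12.4). Scoping may therefore vary by site, therapy and visit. Differences in activity class between treatment patterns, or over time, would then partly reflect who was scoped. Protocol 15.2.5 and SAP 8.4 plan no assessment of missing-data patterns, so the analysis would not reveal this.

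The SAP 7.4 bands raise a different question. A reader who knows the Appendix 3 classes cannot recover them from these bands. For partial Mayo, the subgroups do not cleanly separate mild from moderate disease in a study of moderate-to-severe inflammatory bowel disease.

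**Working it through.** **Inputs.** Four subscores, of which Appendix 3 says "Each parameter of the score ranges from zero (normal or inactive disease) to 3 (severe activity". The two class tables are those of Appendix 3, and the bands are those of SAP 7.4.

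**The plan's own figure.** The maximum full score is 4 × 3 = 12 and the maximum partial score is 3 × 3 = 9. Both agree with Protocol 4.3.

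**Enumeration.** There are 4 × 4 × 4 × 4 = 256 subscore sets, made of 64 clinical profiles (stool frequency, bleeding, physician's global assessment) times four endoscopy grades. Each set was classed by partial score = stool + bleeding + global, and by full score = partial + endoscopy, using the matching table.

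| Partial total | Clinical profiles | Partial class | Full class, endoscopy 0 | Endoscopy 1 | Endoscopy 2 | Endoscopy 3 | Sets that differ | SAP 7.4 band |
|---|---|---|---|---|---|---|---|---|
| 0 | 1 | remission | remission | remission | no class | mild | 2 | 0 |
| 1 | 3 | remission | remission | remission | mild | mild | 6 | 1–2 |
| 2 | 6 | mild | remission (3) or no class (3) | mild | mild | mild | 6 | 1–2 |
| 3 | 10 | mild | mild | mild | mild | moderate | 10 | 3–5 |
| 4 | 12 | mild | mild | mild | moderate | moderate | 24 | 3–5 |
| 5 | 12 | moderate | mild | moderate | moderate | moderate | 12 | 3–5 |
| 6 | 10 | moderate | moderate | moderate | moderate | moderate | 0 | ≥6 |
| 7 | 6 | moderate | moderate | moderate | moderate | moderate | 0 | ≥6 |
| 8 | 3 | severe | moderate | moderate | moderate | severe | 9 | ≥6 |
| 9 | 1 | severe | moderate | moderate | severe | severe | 2 | ≥6 |

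**Point 1, full against partial.**
- Sets that differ: 2 + 6 + 6 + 10 + 24 + 12 + 0 + 0 + 9 + 2 = 71, and 71/256 = 27.7%. The other 185 agree.
- By type (partial class, then full class): 34 mild/moderate, 12 moderate/mild, 11 severe/moderate, 7 remission/mild, 3 mild/remission, and 4 with no full-score class.
- The full class is higher in 34 + 7 = 41 sets and lower in 12 + 11 + 3 = 26, so the shift has no single direction.
- The 4 unclassed sets have a full score of 2 made up of one subscore of 2. They fail the remission condition and lie below the mild range.
- Only partial totals 6 and 7 (10 + 6 = 16 of 64 profiles) keep their class whatever endoscopy shows.
- Restricting to the 46 sets whose subscores all lie within one point of each other, 9 still differ (9/46 = 19.6%).

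Example: stool 1, bleeding 0, global 1 is partial 2, mild. With a normal endoscopy it is full 2, remission. Stool 3, bleeding 2, global 3 is partial 8, severe. With endoscopy 2 it is full 10, moderate.

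**Point 2, SAP 7.4 against the Appendix 3 partial table.** SAP 7.4 cuts between 0 and 1, 2 and 3, and 5 and 6. Appendix 3 cuts between 1 and 2, 4 and 5, and 7 and 8. No cut coincides.
- Band 0 is purely remission.
- Band 1–2 mixes remission (1) with mild (2).
- Band 3–5 mixes mild (3–4) with moderate (5).
- Band ≥6 mixes moderate (6–7) with severe (8–9).

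Two of the SAP cuts, 2/3 and 5/6, equal cuts in the full-score table. The documents do not say whether that is intended.

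**The case against.** Several stronger readings are tempting and do not hold.

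- **That means over visits would mix a 0–12 and a 0–9 scale.** No available text says the versions share one mean or one class variable. SAP 8.1.3 refers to example tables for its layout, and those pages were not available. They may separate the versions. Reporting each version by its own Appendix 3 table is also a natural reading of the Study summary. That reading does not remove point 1: if each patient is reported under the version scored, the class still follows scoping.
- **That the SAP 7.4 subgroups depend on endoscopy.** They use the partial score only, so they cannot.
- **That the Harvey-Bradshaw bands in SAP 7.4 share the fault.** The 5–16 band merges two whole adjacent Appendix 4 classes and crosses no boundary.
- **That treat-to-target remission is affected.** Protocol 4.4 defines it by symptom resolution and the endoscopic subscore, not by Mayo total class.
- **That 28% of patients would be misclassed.** The count weights all combinations equally, including implausible ones, and the documents give no score distribution.

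Some further points stand as limits. The study is descriptive, and activity is one of five breakdowns in SAP 8.1.2. The SAP 7.4 bands carry no severity labels and serve exploratory subgroups, so using other strata is not in itself forbidden. Some disagreement between versions is expected, because the full score adds information.

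**Conclusion.** Two separate points stand.

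First, the protocol accepts either Mayo version, its two tables disagree for 71 of 256 subscore combinations (4 of them without a full-score class), and the available SAP text names no version for its 8.1.2 and 8.1.3 tables. UC activity class can therefore depend on whether endoscopy was done. The effect in patients cannot be sized from the documents. It requires that scoping differ between the groups or visits compared, which the design allows but the documents do not quantify.

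Second, and independently, three of the four SAP 7.4 partial-Mayo bands straddle Appendix 3 partial boundaries. No rationale appears in the available text, although the SAP Introduction asks that discrepancies from the protocol be explained.

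The reach is the description of activity, the activity breakdown of treatment patterns, and the first-line subgroups. Confidence is moderate, because the example tables could not be seen. No view is taken on which cut-offs are clinically right.

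**What to change.** **SAP 8.1.2 and 8.1.3.** Make the partial Mayo, with the Appendix 3 partial cut-offs, the main UC activity class at every visit wherever the three clinical subscores are available. Report how many patients lack them at each visit. Some may: Protocol 12.3 and 12.4 list stools per day, whereas the Mayo item scores stools above the patient's normal number, and they also allow other activity scales. Show the endoscopic subscore as its own variable, and the full Mayo only as a supplementary table in scoped patients, stating how the unclassed full score of 2 is shown. Never combine the two versions in one mean or one class. With one version used throughout, discordance from the choice of version falls from 71 of 256 to 0.

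**SAP 7.4.** Reconcile the partial-Mayo bands with the Appendix 3 partial classes (<2, 2–4, 5–7, >7), merging only whole adjacent classes if cells are sparse. Otherwise state the rationale for departing from them.

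**Cost.** SAP wording and programming, with the change recorded in the final report as SAP 8.5 asks. No new data collection is proposed. The downside is that endoscopic information leaves the main activity class, and patients without all three clinical subscores appear as unclassified.

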10.1 Overall study design

This is an international, retrospective and prospective, multicentre, non-interventional, observational study. This study is a 'non-interventional study' as defined in EU Clinical Trial Regulation No. 536/2014 [23] and the guidelines for GVP [21]. This means that:

- the medicinal product(s) is (are) prescribed in the usual manner according to local routine practice,
- the assignment of a patient to a particular therapeutic strategy is not decided in advance by the study protocol but falls within current practice;
- the prescription of the medicine is clearly separated from the decision to include the patient in the study;
- no additional diagnostic or monitoring procedures shall be applied to the patients;
- epidemiological methods shall be used for the analysis of collected data.

A prospective design of the study means that patients that have been enrolled according to criteria inclusion and exclusion and signed the Informed Consent form will be observed in the future.

In the retrospective part of the study all data will be collected from past records of patients' source documents. Retrospective design means that all patients' data that will be collected in the study were recorded in the patients' file prior to the date when Informed Consent form is signed (in scope of investigator's responsibility about data confidentiality and data protection described in the study protocol).

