 - Disease extent according to the following Montreal Classification categories;
 - Systemic (extra intestinal) IBD manifestations;
 - IBD complications;
 - Vaccination in accordance with IBD treatment guidelines.
- Disease activity data at baseline visit will consist of specified signs and symptoms depending on the disease type:
 - CD: abdominal pain severity, number of liquid stools per day, presence of an abdominal mass, endoscopic findings (if done), documented presence of CD

complications, and Harvey Bradshaw Index or other documented disease activity scales (if applicable).

- UC: frequency of stools/day, rectal bleeding, endoscopic findings (if done), physician global assessment of disease severity, and Mayo scores or other documented disease activity scales (if applicable).
- IBD status at baseline visit:
 - IBD status as judged by investigator (remission, incomplete remission, flare, others), nature of remission at the time of examination;
 - IBD flare(s);
- Laboratory and instrumental evaluation of IBD for the last 2 years and at the time of the baseline visit (if done within routine practice) - for details please section 12.8;
- IBD treatment:
 - IBD treatment for the last 2 years and at the time of the baseline visit;
 - IBD surgical treatment for the last 2 years and at the time of the baseline visit;
- Healthcare resources utilization for the last 2 years and at the time of the baseline visit;
- Concomitant treatment.

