12.4 Data collected at the Observational visit (V2) and Final Visit (V3)

Data to be collected directly on Observational visit (V2) and Final visit (V3):

- Date of visit (day, month, year)
- Type of visit: visit to physician office or distant contact
- Physical examination: weight (kg), body mass index calculation;
- IBD assessment at the time of the visit:
 - Disease extent according to the following Montreal Classification categories;
- Disease activity data at the visit will consist of specified signs and symptoms depending on the disease type:
 - CD: abdominal pain severity, number of liquid stools per day, presence of an abdominal mass, endoscopic findings (if done), documented presence of CD complications, and Harvey Bradshaw Index or other documented disease activity scales (if applicable).
 - UC: frequency of stools/day, rectal bleeding, endoscopic findings (if done), physician global assessment of disease severity, and Mayo scores or other documented disease activity scales (if applicable).
- IBD status (with current/last available data by the date of the visit):

- IBD status as judged by investigator (remission, incomplete remission, flare, others), nature of remission at the time of examination;
- IBD flare(s);
- Systemic (extra intestinal) IBD manifestations;
- IBD complications;
- Vaccination in accordance with IBD treatment guidelines.
- Laboratory and instrumental evaluation of IBD (if done within routine practice) - for details please section 12.8;
- IBD treatment;
- IBD surgical treatment;
- Healthcare resources utilization;
- Concomitant treatment
- Adverse events and adverse drug reactions (seriousness, severity, causality, start and stop dates, action, frequency, outcomes):
 - adverse drug reactions on IBD treatments,
 - adverse events on Entivyo® (Vedolizumab) treatment,
 - serious adverse events on IBD treatments (including Entivyo® (Vedolizumab) treatment).

All adverse events and adverse drug reactions must be documented on the Adverse Report Form which is appended to the Case Report Form.

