14.1.3. Protocol Deviations

The investigator should not deviate from the protocol, except where necessary to eliminate an immediate hazard to study patients. In accordance with NIS definition all examinations and other data should be registered in the CRF only if they are done in routine practice.

Should other unexpected circumstances arise that will require deviation from protocol-specified procedures and data collections rules, the investigator should consult with the Sponsor, responsible CRO or designee (and IRB or IEC, as required) to determine the appropriate course of action. There will be no exemptions (a prospectively approved deviation) from the inclusion or exclusion criteria.

In the event of a significant deviation, the site should notify the sponsor or its designee (and IRB or EC, as required). Significant deviations include, but are not limited to, those that involve fraud or misconduct, or confound interpretation of primary study assessment.

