#### Secondary endpoints (outcomes):

- Distribution of socio-demographic variables in patients with moderate to severe UC/CD treated with biologics or/and non-biological treatment;
- Distribution of clinical variables in patients with moderate to severe UC/CD treated with biologics or/and non-biological treatment. Clinical characteristics include family history of IBD, smoking habits (no smoker, ex-smoker and current smoker), medical history comorbidities, disease characteristics (age of disease onset, location of disease, clinical course, disease severity, intestinal and systemic (extraintestinal) manifestations, complications in history and during the study observational period, etc.);
- Description of methods used for documentation of disease activity in routine practice (incl. clinical, endoscopic, lab, histological), and frequency of objective CD/UC disease activity assessment using different methods;
- Percentage of moderate to severe IBD patients achieved clinical and combined clinical and endoscopic remission (based on T2T definitions);
- Percentage of patients with moderate to severe IBD with at least one episode of failure of biological therapy or/and non-biological therapy (e.g., dose escalation of biologics, switching to another therapy, IBD-related surgery, medication augmentation);
- Patterns of treatment decisions\actions made after making the clinical assessment of IBD activity (incl. therapeutic de-escalation, escalation, without changes) depending on scenario of achievement /non-achievement of T2T treatment goals;
- Challenges of implementing a T2T strategy in UC and CD in real clinical practice (incl. clinicians related factors, patient related factors, disease related factors);
- Healthcare resources utilization for patients with moderate to severe UC/CD: hospitalizations due to complications, IBD related surgeries, disability determination

Protocol ID	MACS-2017-102279	STATISTICAL ANALYSIS PLAN	Page 16 of 41	
IP	N/A		Date	30.12.2021
ID	MACS-2017-102279_SAP		Version	v1.2 final

(frequency, percentage of UC and CD patients, who used these healthcare resources) within 2 years before enrolment and during 12-months observational period;

- Percentage of UC and CD patients with surgical treatment in 2 years history and during 12-months observational period in frames of this study: indications, types of surgeries, complications.

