**The same information will be provided for the treatment pattern (if the corresponding treatment pattern will be large enough to make statistical inferences).**

As treatment pattern change over time, patterns will be assessed for certain time points and the change of patterns will be tracked throughout the study (see also example Table 8):

- Retrospective treatment pattern (change assessment for every 6 months of the 2-year treatment interval);
- Treatment pattern between the date of enrollment and 6 months;
- Treatment pattern between 6 and 12 months.

Accordingly, for each above-mentioned period, each pattern will be assessed for the history of changes (see example Table 8):

- Presence of dose modifications;
- Presence of discontinuations / treatment changes;
- Presence of flares (during the course of treatment);
- Add-on therapy.

Protocol ID	MACS-2017-102279	STATISTICAL ANALYSIS PLAN	Page 26 of 41	
IP	N/A		Date	30.12.2021
ID	MACS-2017-102279_SAP		Version	v1.2 final

In order to track the history of transition of subject “states” (i.e. treatment using the certain pattern from the list above), in addition to the descriptive 6-monthly data, transition state (Sankey) diagrams will be built (see Figure 2 for mock example) to visualize the subject journey across patterns as well as trends of pattern change over time.

Treat-to-target (T2T) success will be assessed (in this SAP) using EDC data, based on the definition of failure to meet T2T goals (*lack of clinical and endoscopic remission based on investigator's feedback and objective methods of evaluation*). Overall T2T success or failure will be analyzed separately from this SAP using Investigator Survey data.

T2T treatment factors will be assessed by Visits 1, 2 and 3 and will be grouped by:

- Clinician-related factors:
  - Frequency and methods of assessment of UC/CD disease activity;
- Patient-related factors:
  - Demographic data;
  - Time frame between the date of first symptom(s) and the date of IBD diagnosis;
  - Smoking status;
- Disease-related factors:
  - Age of disease onset;
  - Location of disease;
  - Clinical course;
  - Disease severity;
  - Presence of intestinal and systemic (extraintestinal) manifestations;
  - Presence of complications;
  - Surgical treatment.

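### Mayo/HBI scores at V1–V3 cannot be read as routine use: Protocol 4.3 conflicts with 10.1, 12.3, 12.4 and 14.1.3, and the SAP does not separate study-prompted from routine scores

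*Protocol*

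**What the plan says.** **Text that reads as a requirement.** Protocol 4.3 says of Crohn's disease that "HBI will be evaluated at each study visit", with no condition. For ulcerative colitis it says "The full or partial Mayo score (in accordance with routine clinical practice) will be evaluated at each study visit". The bracket follows the words on full or partial, and most naturally governs that choice.

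**Text that points to routine practice only.** Protocol 10.1 defines the study as one in which "no additional diagnostic or monitoring procedures shall be applied to the patients". Protocol 12.3 and 12.4 list, for CD, "Harvey Bradshaw Index or other documented disease activity scales (if applicable)" and, for UC, "Mayo scores or other documented disease activity scales (if applicable)". Protocol 14.1.3 says that "all examinations and other data should be registered in the CRF only if they are done in routine practice".

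**Where the result is used.** SAP 6.1 has as a secondary endpoint: "Description of methods used for documentation of disease activity in routine practice (incl. clinical, endoscopic, lab, histological), and frequency of objective CD/UC disease activity assessment". SAP 8.1.3 lists one clinician-related treat-to-target (T2T) factor: "Frequency and methods of assessment of UC/CD disease activity". SAP 8.7 names the Mayo and Harvey-Bradshaw indices among the objective methods of assessment.

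**The concern.** The endpoint is meant to describe what physicians do unprompted. If the study itself asks for an index at each visit, a physician who never scores one in ordinary care looks the same, at V1–V3, as a physician who always does. The clinical-index part of the endpoint, and of the clinician-related T2T factor, would then measure compliance with the protocol. Protocol 5.2 says that the study should help to reveal gaps in care, and low use of activity indices is one gap that such a table could hide.

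Nothing in the SAP lets the analyst tell the two kinds of score apart. It does not say whether visit scores enter the frequency table, and no item marks a score as prompted by the study.

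**Working it through.** This is mainly a check of text against text. The plan gives no figure for how often indices are scored, so there is none to reproduce. Its one design figure, the precision for treatment failure in CD patients on biologics, does reproduce: 2000 × 0.40 × 0.40 = 320; 320 × 0.90 = 288; 1.96 × √(0.5 × 0.5 / 288) = 5.77 points, against the stated 5.8. It has no bearing on this point.

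**Step 1. Do the sections agree?**

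| Source | What it implies for Mayo/HBI at V1–V3 |
|---|---|
| Protocol 4.3 | Scored at each visit; no condition for HBI |
| Protocol 12.2 and SAP Table 1 | Disease activity row marked at V1, V2 and V3; the routine-practice footnote sits on the laboratory and instrumental row only |
| Protocol 12.3, 12.4 | These indices or another documented scale, if applicable; it is unclear whether that condition covers the indices or only the other scales |
| Protocol 10.1 | No added monitoring |
| Protocol 14.1.3 | Recorded only if done in routine practice |

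A site cannot satisfy both 4.3 and 14.1.3 for a patient it would not otherwise score.

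**Step 2. Does 12.4 settle it?** No. Its lists attach an if-done condition to endoscopic findings. They attach none to stool frequency, rectal bleeding or the physician's global assessment, which are the three partial Mayo components (Appendix 3). Four of the five HBI parameters are listed for CD in the same way (all but well-being, Appendix 4). Even if the index is optional, most of its inputs are not marked so.

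**Step 3. Is there a comparison outside the visits?** The disease activity row has no retrospective mark. The IBD assessment row does, but 12.3 fills it with Montreal extent, extraintestinal manifestations, complications and vaccination, and no index. Index scores are therefore not clearly scheduled for the two years before enrolment, although the secondary objective on how and when activity is assessed covers them.

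**Step 4. What could the distortion look like?** Illustration only. Let q be the chance that a physician would score at a visit without the study, independent between visits. The documents give no value; 0.2 to 0.8 is an assumed range. If 4.3 is followed, a patient scored at all three visits has 3 scores. Under routine practice the expected number is 3q, and the chance of at least one is 1 − (1 − q)³.

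| q (assumed) | Expected routine scores, 3q | Ratio 3/(3q) | At least one score, routine | Gap to 100% (points) |
|---|---|---|---|---|
| 0.2 | 0.6 | 5.0 | 48.8% | 51.2 |
| 0.4 | 1.2 | 2.5 | 78.4% | 21.6 |
| 0.6 | 1.8 | 1.67 | 93.6% | 6.4 |
| 0.8 | 2.4 | 1.25 | 99.2% | 0.8 |

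If sites followed 12.4 and 14.1.3 as limits on recording, the distortion does not arise. The result depends on which instruction each site applied, and the database does not record that.

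**The case against.** The strongest reply is that 4.3 sits in the chapter on abbreviations and definitions, while section 12 says what is collected and 14.1.3 applies to all data. Read as a whole, a non-interventional protocol that bars added procedures arguably asks sites only to record the scores they already make. The Mayo sentence itself mentions routine practice. This stands as a reason not to treat the requirement as settled. It does not remove the conflict, because the HBI sentence is unconditional and the schedule footnote does not reach the disease activity row.

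A reader might infer that the study fixes scoring at 100%, with three scores for every patient who completes V2 and V3. The documents do not support that. Protocol 12.4 allows V2 and V3 to be distant contacts, HBI includes an abdominal mass item that is hard to obtain remotely, other scales are allowed, and missing data are not imputed.

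A reader might also infer that nothing outside the visits is observed. That too goes too far. SAP 8.7 lists assessment frequency and methods for the 2019 interim analysis over the two retrospective years, and SAP 5.3.3 collects results of diagnostic methods continuously between visits. Whether index scores are among those data is unclear, which is not the same as absent.

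Finally, the scope is narrow. The Physician Survey also asks about use of objective measures, and SAP 8.1.3 leaves overall T2T success to a separate analysis of survey data.

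**Conclusion.** The point holds as an unresolved contradiction with no rule in the SAP to handle it. Where sites followed 4.3, the Mayo/HBI frequency at V1–V3 reflects the protocol; where they followed 14.1.3, it reflects practice. The pooled figure mixes the two and cannot be interpreted as routine use.

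The size cannot be known from the documents. The ratios of 1.25 to 5 above rest on an assumed scoring rate, on independence between visits and on full adherence to 4.3, so they show direction and possible range only. That the study sets the frequency everywhere is not established.

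The effect is confined to the clinical-index component of one descriptive secondary outcome and of the clinician-related T2T factor. Endoscopic, laboratory, imaging and histological frequencies are recorded only if done in routine care and are not affected. The correction is still worth making, because it is cheap and changes what may be concluded about index use.

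**What to change.** 1. Reconcile Protocol 4.3 with 12.3, 12.4 and 14.1.3, so that it is clear whether an index is scored at each visit or recorded only when routine care produces it.
2. In SAP 8.1.3, leave Mayo/HBI scores from V1–V3 out of the routine-practice assessment-frequency outcome and out of the clinician-related T2T factor. Alternatively, show them in a separate row labelled as study-visit scores that do not estimate routine use.
3. Base the routine-practice frequency on dated endoscopy, CRP, calprotectin, imaging and histology. Protocol 12.7 collects such examinations retrospectively, at baseline and through the prospective year.
4. Keep the visit scores for the planned disease-activity and remission tables.

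For the analysis this costs SAP wording and no new data. The price is that visit data then give no estimate of routine clinical-index use.

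Two further steps are not worth proposing. A new eCRF item to flag study-prompted scores comes too late to be cheap: SAP v1.2 is dated 30.12.2021, and Protocol 10.2 plans the end of data collection for Q3–Q4 2021. A count of indices from the two years before consent would need new extraction, because the schedule does not mark those data for retrospective collection.
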